## 6.2 Randomisation

Subjects will be allocated to a condom use regime (one of six treatment sequences in a fixed block size) according to a computer-generated randomisation schedule produced by the CRO.

A randomisation schedule will be generated for 204 kits to account for dropouts, overage, replacement and additional randomisation codes for IMSU retention samples (which will be retained at Reckitt).

Randomised subjects will be numbered sequentially.

## 6.3 Administration of Medical Device

Subjects will not be given the full condom kit to take away with them. Following randomisation each subject will be given one of the condom cartons from their kit (as per randomisation schedule). This will contain 8 condoms. Each condom must be used for penile-vaginal intercourse only. To mitigate double exposure to benzocaine, subjects will be instructed to use one investigational condom for each coital act. Each coital act must be at least 24 hours apart. During this 24-hour interval, subjects and their female partners will be instructed to refrain from any sexual activity including masturbation. In the situation of condom breakage or condom slippage, subjects may continue to have intercourse without the investigational condom only if they believe they are not at risk of an STI or pregnancy.

On return to the clinical site for the subsequent visit, subjects should return all unused condoms. They will then be given the second condom carton from their kit according to the randomisation schedule, containing 8 condoms of the second condom type to be used during the second condom assessment period (4 weeks). This is to be repeated for subjects to complete use of their third condom type.

Subjects will be trained in the use and handling of the condoms (verbally and written format). Subjects will be instructed to record IELT, the duration from the start of vaginal entry (vaginal penetration into the female partner) till the start of intravaginal ejaculation (release of semen), for each condom used.

During the clinical investigation, subjects are permitted to use lubricant if needed. Subjects should make the clinical site aware of this through questioning by the clinical site staff. Any use of lubricant will be recorded in the IELT diary.

## 6.4 Demographics

Baseline characteristics and demographic information will be recorded. This will include:

1. For male subjects and their female partners:
  - Sex
  - Age
2. For male subjects only:

	Clinical Investigation Plan		
	Investigation No: 5078401	Protocol Version: V2.0 08-Jun-2023	Page 38 of 62

- Ethnicity
- Height (in metres to the nearest cm)
- Weight (kg to the nearest 0.1 kg; in indoor clothing and without shoes).

BMI will be calculated as follows: Body weight (kg)/ [Height (m)].

## 6.5 Medical History and Prior Therapies

Details of all relevant current and historical medical diseases, conditions or surgeries, including duration, will be recorded for subjects and their female partners. All prior therapies such as prescription or non-prescription drugs, including vitamins, herbal and dietary supplements and non-pharmacological treatments such as physiotherapy will also be recorded. Medical history for all prior therapies should be recorded, regardless of being relevant. In addition, the contraception method will also be recorded.

## 6.6 Physical Examination

For male subjects, a complete physical examination, including a penile examination, will be performed by the Investigator or a medically qualified delegate (e.g. Principal Investigator/ Co-Investigator). The Investigator or delegate may conduct physical examination of female partners in any case of AE/ ADE or in the opinion of the Investigator.

The examination will include at least general appearance, skin/ subcutaneous tissue, ears/ eyes/ nose/ mouth/ throat, head/ neck, respiratory/ chest, cardiovascular, gastrointestinal, musculoskeletal, neurological, lymph nodes and penile examination. Other body systems can be examined if required, at the discretion of the Investigator or delegate. The Investigator or delegate will provide an interpretation of the results. Clinically significant abnormalities will be recorded on the medical history at screening or AE/ ADE page of the eCRF.

## 6.7 Vital Signs

For male subjects, vital signs will be measured after the subject has been seated for approximate 5 minutes and include the following:

- Blood pressure (systolic and diastolic; mmHg)
- Heart rate (radial pulse counted for 30 seconds; beats/ minute)
- Oral or tympanic body temperature (°C)

The Investigator or delegate will provide an interpretation of the results. Clinically significant abnormalities will be recorded on the AE/ ADE page of the eCRF.

## 6.8 Pregnancy Test

Urine samples for pregnancy testing (for subject's female partner of childbearing potential only) will be collected and prepared according to the test kit instructions.

	Clinical Investigation Plan		
	Investigation No: 5078401	Protocol Version: V2.0 08-Jun-2023	Page 39 of 62

## 6.9 Sexual Intercourse Self-Estimation Scale

Subjects will be asked to verbally rate the scale. The question and the scale are:

Thinking of any sexual intercourse you have had over the past 12-months, how often do you feel intercourse ended early due to earlier than desired ejaculation?

- 1 = Never
- 2 = Occasionally (now and then/irregularly)
- 3 = Frequently (often/regularly)
- 4 = Every time

Subjects that rate a score of 2 (Occasionally) would meet the inclusion criterion. Anyone who selects the score of 1 (Never), 3 (Frequently) or 4 (Every time) would not meet the inclusion criterion of the investigation. Those who answer 3 (Frequently) or 4 (Every Time) will be advised to seek opinion from his healthcare provider as there may be a missed diagnosis of PE.

## 6.10 Diary and Questionnaires

### 6.10.1 Intravaginal Ejaculation Latency Time (IELT) Diary

Each subject will be asked to complete an IELT diary to record the IELT duration record for each condom use within 2 hours after each coital act (per condom type). Subjects will also be instructed to record condom failure (breakage or slippage) and any use of lubricant in the diary.

### 6.10.2 EMSEX Pleasure Scale

Each subject will be asked to complete an EMSEX pleasure scale for each condom use within 2 hours after each coital act (per condom type). EMSEX pleasure scale is a 11-item scale which assesses sexual pleasure at the event level (Aaron et al, 2018). For each item, the range spans the entirety of the potential range from 0 (zero) to 100 (one hundred).

### 6.10.3 Patient Global Impression of Change (PGIC)

Upon completion of each condom assessment period, each subject will be required to complete a PGIC. PGIC is a patient-reported scale which assesses the subject's perception of improvement in terms of 'lasting longer' since using the condoms (Althof et al, 2010). The PGIC is a 7-point response scale (Very much better, Better, Little better, No change, Little worse, Worse, Very much worse) to ask subjects how they describe the change in their ejaculation time in each assessment period.

### 6.10.4 Subject Perceived Questionnaire (SPQ)

Upon completion of each condom assessment period, each subject will be required to complete a SPQ. The questionnaire will collect the following information (including, but not limited to): experience with condom use, acceptability, preference and tolerability.

	Clinical Investigation Plan		
	Investigation No: 5078401	Protocol Version: V2.0 08-Jun-2023	Page 40 of 62

## 6.11 Adverse Events

During visits to the clinical site non-leading questions will be used to collect any AEs/ ADEs. In addition, spontaneously reported AEs/ ADEs will be collected.

The observation period for an individual subject and his female partner will start after giving informed consent and will finish at the last visit (follow-up visit). All AEs/ ADEs that arise during the observation period will be recorded and an assessment of the AEs/ ADEs will be performed as per [Section 8.2](#) by a medically qualified Investigator. If a subject or his female partner has an AE/ ADE that is still ongoing at the last visit, an attempt will be made by the Investigator to follow this up as per [Section 8.4](#).

If an untoward medical occurrence happens after the subject has signed the consent form but before administration of the device, it should be reported as an AE, including those associated with investigation procedures.

## 7 INVESTIGATION PROCEDURES BY VISIT

### 7.1 Investigation Flow Chart / Table of Investigation Procedures and Assessments

**Table 7-1 Schedule of Assessment**

Visit	Visit 1	Visit 2	Visit 3 & 4	Visit 5
Period	Screening Baseline Period	Assessment Period 1	Assessment Period 2 & 3	Follow-up
Procedure \ Day	Within 28 days prior to Day 1	Day 1	Within 7 days after each condom assessment period	Within 7 days after 3 rd condom assessment period
Informed consent	X			
Inclusion / Exclusion 	X	X	X	
Demographics	X			
Medical history & prior therapies	X			
Concomitant medication	X	X 	X 	X 
Vital signs	X			X
Physical examination 	X	X	X	X
Pregnancy test  (subject's female partner)	X	X	X	X
Randomisation		X		

	Clinical Investigation Plan		
	Investigation No: 5078401	Protocol Version: V2.0 08-Jun-2023	Page 41 of 62

Visit	Visit 1	Visit 2	Visit 3 & 4	Visit 5
Period	Screening Baseline Period	Assessment Period 1	Assessment Period 2 & 3	Follow-up

 

 
Day
 
Procedure
 
	Within 28 days prior to Day 1	Day 1	Within 7 days after each condom assessment period	Within 7 days after 3 rd condom assessment period
Provide investigation stopwatch	X			
Dispense Investigational Product 		X	X	
Collect returned Investigational Product 			X	X
Collect returned investigation stopwatch				X
Stopwatch measure and condom use training 	X	X	X	
Provide IELT diary, EMSEX pleasure scale, PGIC and SPQ	X 	X	X	
Completion of IELT diary	X	X	X	
Completion of EMSEX pleasure scale, PGIC  and SPQ 		X	X	X
Review for extent of completion of diary and questionnaires		X 	X	X
Adverse Events & Adverse Device Effects and Device Deficiencies	X 	X 	X 	X 

1. Eligibility will be confirmed at visit 1 as part of the screening visit. Continued eligibility will be confirmed at each assessment visit (visit 2, 3 and 4).
2. At visit 1, subjects will undergo a penile examination as part of the physical examination. At visit 2, 3, 4 and 5 (assessment period visits and follow-up visit) these will only be performed if necessary in the opinion of the Investigator. The Investigator may conduct physical examination of female partners in any case of AE/ ADE or in the opinion of the Investigator.

	Clinical Investigation Plan		
	Investigation No: 5078401	Protocol Version: V2.0 08-Jun-2023	Page 42 of 62

3. Subject's female partner of childbearing potential must have a negative pregnancy test at Screening. In cases where subjects have experienced a condom breakage or slippage, their female partner may be subject to a pregnancy test, if deemed necessary by the investigator.
4. Subjects will be provided their allocated condoms (condom type in accordance with the randomisation schedule) at visits 2, 3 and 4. Lubricant will also be supplied, if requested by subjects.
5. Any unused condoms will be returned to the clinical site on visits 3, 4 and 5. All used and unused lubricant will be returned to the clinical site on visit 5.
6. At visit 1, subjects and their female partners will be trained on the stopwatch process and the correct use of the condoms. At visit 2, 3 and 4 (assessment period visits) the training will only be performed if necessary in the opinion of the Investigator.
7. IELT Diary only.
8. PGIC and SPQ can be completed at home or at the next visit.
9. Excludes ADEs and Device Deficiencies.
10. In addition to male subjects' data collection, concomitant medication and AE/ ADE of female partners will be collected through spontaneous reporting or in response to non-leading question to the subject on visit 2, 3, 4 and 5 or observation by the Investigator.

## 7.2 Visit 1: Screening Visit and Baseline Period

At the screening visit, which will be carried out within 28 days prior to subjects receiving their first condom type, subjects and their female partners will be asked to provide written informed consent (separately) for the participation in the clinical investigation.

Once informed consent has been obtained, the subjects will be issued a screening number. Clinical assessments consisting of demographics, medical history, prior therapies, vital signs recording, physical examination, concomitant medication, AEs will be carried out for each subject. Medical history, prior therapies, concomitant medication and AEs for the female partners will be assessed as well as urine pregnancy test for women of childbearing potential.

Clinical site staff will explain to each subject and his female partner the stopwatch process and how to measure the IELT i.e. that the duration of the IELT is calculated from time of vaginal entry (vaginal penetration into the female partner) until the start of intravaginal ejaculation (release of semen) and is timed on the stopwatch by 'start' (penetration) to 'stop' (ejaculation) and to record in the IELT diary. It will be made clear by the clinical site staff that either partner can be responsible for using the stopwatch as long as it's the same person each time. They will also be requested to note the date and time of the act in the IELT diary. An investigation stopwatch together with the training on stopwatch measures will be provided to ensure there is an understanding of when to 'click' the stopwatch and that the subjects or their female partner are capable of accurate measurements. Training (verbally and written format) in the correct use of the condoms will also be provided. Subjects and their female partners will be informed that should they experience a condom failure, including breakage and slippage, and believe that they are at risk of pregnancy, they should contact the clinical site where they will be provided with access to emergency contraception and the appropriate follow-up (if necessary). If either partner believes they may have contracted an STI they should contact the clinical site where appropriate measures, and follow-up will be taken.

Subjects will be trained by the clinical site staff on how to complete IELT diary, EMSEX pleasure scale, PGIC and SPQ.

Subjects and their female partners are required to confirm they are using an acceptable method of contraception as listed in inclusion criteria 9 and the contraception method will be entered into each subject's eCRF. Subjects and their female partners will return home to begin the baseline period.

	Clinical Investigation Plan		
	Investigation No: 5078401	Protocol Version: V2.0 08-Jun-2023	Page 43 of 62

Subjects will be instructed to complete an IELT diary within 2 hours after each coital act and to report a minimum of 4 IELT duration records over the 4-week baseline period. Each coital act must be at least 24 hours apart. During this 24-hour interval, subjects and their female partners will be instructed to refrain from any sexual activity including masturbation.

During the baseline period, subjects and their female partners will be protected from pregnancy by means of their second form of contraception. If the subject or his female partner feels there is at risk of a STI or there is any safety concern, they will be instructed to use commercial condom as well as commercial lubricant if desired for an intercourse. The commercial condom and commercial lubricant, which are not provided by the clinical site, should be non-medicated and should not have any performance enhancing functionality. The use of condom and lubricant will be reported by the subject in the IELT diary.

The female partners will be instructed that they can contact the clinical site to report an AE/ ADE or to discuss any concern during their participation in this clinical investigation.

All assessments conducted during the screening visit are detailed in [Section 6](#) and summarised in [Table 7-1](#). All clinical assessments and test results will be entered into each subject's eCRF.

### 7.3 Visit 2: Assessment Period 1

Subjects who fulfil all the eligibility criteria and have reported a minimum of 4 IELT duration records will return to the clinical site for assessment period 1. Clinical assessments consisting of a physical examination (if necessary in the opinion of the investigator) will be carried out.

Following confirmation of continued eligibility, subjects will be randomised as to which condom type they will receive first. Subjects will be assigned a randomisation number. Subjects will be given a carton containing their allocated condom type for use, with the second and third carton remaining in the kit at the clinical site. Lubricant will be made available to subjects who routinely use lubricant during intercourse or if requested.

The Investigator or delegate will examine the diaries for completeness. Training on stopwatch measure, the correct use of the condoms and the clinical investigation requirements will be provided if necessary in the opinion of the Investigator. Subjects will be reminded to complete an IELT diary and EMSEX pleasure scale with 2 hours after each coital act and to report a minimum of 4 IELT duration records within a maximum 4-week period (known as the condom assessment period). Each coital act must be at least 24 hours apart. During this 24hour interval subjects will be instructed to refrain from any sexual activity including masturbation. For all used condoms, subjects will be instructed to dispose them into a bin.

Subjects will also be instructed to complete a PGIC and a SPQ at the end of each condom assessment period. PGIC and SPQ can be completed at home or at next visit. Subjects will be reminded that should he and his female partner experience a condom failure and believe that they are at risk of pregnancy, they should contact the clinical site where they will be provided with access to emergency contraception and the appropriate follow-up (if necessary). If either partner believes they may have contracted an STI they should contact the clinical site where appropriate measures, and follow-up will be taken. If necessary, in the opinion of the investigator, the female partner will

	Clinical Investigation Plan		
	Investigation No: 5078401	Protocol Version: V2.0 08-Jun-2023	Page 44 of 62

attend the clinical site and a urine pregnancy test will be carried out. In between condom assessment periods, subjects and their female partners will be protected from pregnancy by means of their second form of contraception.

All assessments conducted during assessment period 1 are detailed in [Section 6](#) and summarised in [Table 7-1](#). All clinical assessments and test results will be entered into the subject's eCRF.

#### **7.4 Visit 3 and 4: Assessment Period 2 and 3**

Visits 3 and 4 will be conducted within 7 days after the completion of each condom assessment period weeks (or earlier if the subject has reported a minimum of 4 IELT duration records). A 3-day washout period, where no test condom will be used, is required before subjects attend the clinical site to return unused condoms and be supplied with their subsequent condom type. During the 3-day washout period, coital act is allowed with a 24 hour gap maintained between the last coital act or masturbation and the visit to the clinical site. Procedures and assessments will be the same as those performed in assessment period 1, except for randomisation, which is performed at Visit 2 only.

Subjects will be required to return all unused condoms of the first and second condom type (respectively). Following confirmation of continued eligibility, subjects will be provided with the alternative condom type from the kit to be used for the subsequent condom assessment period. Additional supply of lubricant will also be provided if required and the empty lubricant bottle/tube should be returned.

In the opinion of the Investigator, a subject who fails to remain eligible for the clinical investigation will be withdrawn.

The Investigator or delegate will examine diaries and questionnaires for completeness. Training and instruction on diary and questionnaire completion and safety reminder will be repeated as Visit 2.

All assessments conducted during assessment period 2 and 3 are detailed in [Section 6](#) and summarised in [Table 7-1](#). All clinical assessments and test results will be entered into the subject's eCRF.

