Subjects will attend the clinical site on 5 occasions: one screening visit, three assessment period visits and one follow-up visit. Screening includes a 4-week baseline period, which allows the subject and his partner to familiarise themselves with the use of the stopwatch method and completing IELT diaries. Eligible subjects will return to the clinical site, where they will be randomised and receive the first of the three condom types (according to the randomisation schedule). Subjects will be provided with 8 condoms per condom type. The process will be repeated until all three condom types have been used. The follow-up visit will occur within 7 days after the completion of the final condom assessment period. At least a 3-day washout period, where no test condom will be used, is required before subjects attend the clinical site for visit 3 and visit 4. The 3-day washout period is to mitigate the effects on any residual benzocaine across condom types.

The investigation design is outlined in the schematic below (Figure 3-1).

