**Product return**

- Has the subject returned the investigation stopwatch? [yes/no]
- Specify if not returned [free text]
- Has the subject returned the unused condoms or the empty carton? [yes/no]
- How many unused condoms were returned? [number]
- How many condoms were used? [number]
- Specify if the product was not returned [free text]
- Has the subject returned the used/unused lubricant? [yes/no]
- How many bottles were returned? [number]
- Specify if the product was not returned [free text]

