*Table 14.2.2.12* Descriptive statistics and odds ratio for proportion of subjects who receive an decrease of 4 minutes in IELT in difference to baseline with the 3% Benzocaine condom compared to the standard NRL condom (FAS/PP\*\*)

*Table 14.2.2.13* Results of GLMM for comparisons of proportion of subjects who receive an decrease of 4 minutes in IELT in difference to baseline with the 3% Benzocaine condom against the standard NRL condom (FAS/PP\*\*)

*Table 14.2.2.14* Descriptive statistics and odds ratio for proportion of subjects who receive an decrease of 4 minutes in IELT in difference to baseline with the 5% Benzocaine condom compared to the standard NRL condom (FAS/PP\*\*)

*Table 14.2.2.15* Results of GLMM for comparisons of proportion of subjects who receive an decrease of 4 minutes in IELT in difference to baseline with the 5% Benzocaine condom against the standard NRL condom (FAS/PP\*\*)

*Table 14.2.2.16* Descriptive statistics and odds ratio for PGIC for the 3% Benzocaine condom compared to the standard NRL condom

*Table 14.2.2.17* Results of GLMM for comparisons of PGIC of 3% Benzocaine condom against the standard NRL condom

*Table 14.2.2.18* Descriptive statistics and odds ratio for PGIC for the 5% Benzocaine condom compared to the standard NRL condom

*Table 14.2.2.19* Results of GLMM for comparisons of PGIC of 5% Benzocaine condom against the standard NRL condom

*Table 14.2.2.20* Descriptive statistics for EMSEX for the 3% Benzocaine condom compared to the standard NRL condom

*Table 14.2.2.21* Results of GLMM for comparisons of EMSEX of 3% Benzocaine condom against the standard NRL condom

*Table 14.2.2.22* Descriptive statistics for EMSEX for the 5% Benzocaine condom compared to the standard NRL condom

*Table 14.2.2.23* Results of GLMM for comparisons of EMSEX of 5% Benzocaine condom against the standard NRL condom

*Table 14.2.2.24* Descriptive statistics for SPQs for the 3% and 5% Benzocaine condom as well as the standard NRL condom

*Table 14.2.2.25* Descriptive statistics for total clinical failure rate for the 3% and 5% Benzocaine condom as well as the standard NRL condom

*Table 14.2.2.26* Descriptive statistics for overall proportion of subjects with TE-AE and TE-ADE rate for the 3% and 5% Benzocaine condom as well as the standard NRL condom

*Figure 14.2.2.1* Bar chart of IELT with the 3% Benzocaine condom and standard NRL condom for primary hypothesis (FAS/PP\*)

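### Adverse events are tabulated by condom with no exposure measure, although a condom period may close after four IELT records or run to four weeks; add exposure-adjusted rates beside the proportions

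*Protocol*

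**What the plan says.** **Length of a condom period.** Protocol 7.3 asks for "a minimum of 4 IELT duration records within a maximum 4-week period (known as the condom assessment period"). Protocol 7.4 (Visits 3 and 4) and 7.5 (Visit 5) place the visit within 7 days after the period, "or earlier if the subject has reported a minimum of 4 IELT duration records". Protocol 6.3 describes the second carton as "to be used during the second condom assessment period (4 weeks"), and Protocol 3.2 also speaks simply of a 4-week period.

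**Limits on use.** Protocol 3.1: "Subjects will be provided with 8 condoms per condom type", and "At least a 3-day washout period, where no test condom will be used, is required" before Visits 3 and 4. Protocol 7.2 and 7.3: "Each coital act must be at least 24 hours apart".

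**Safety endpoint.** The proportion of subjects with at least one adverse event or adverse device effect is among the secondary endpoints in Protocol 9.5.2.1. Protocol 9.5.2 says that all secondary endpoints are evaluated by comparing each benzocaine condom with control. The formula in SAP 10.5 divides by all subjects. Table 14.2.2.26 (SAP 19.4) is to show the "overall proportion of subjects with TE-AE and TE-ADE rate for the 3% and 5% Benzocaine condom" and the control. Tables 14.3.1.1 onward give counts and percentages. Protocol 9.6 calls an event treatment-emergent if it began after the first condom was used. It gives no rule for assigning the event to one of the three condoms.

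**Exposure data.** SAP 9.3 (Product return) records "How many condoms were used? [number"]. The diary dates each act (SAP 9.1), and the adverse event form records onset date and time (SAP 9.2). Protocol 9.5.3 plans a summary of intercourse episodes per condom type. For clinical failure, SAP 10.5 does divide by condom usage.

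**The concern.** The time and the number of uses over which events can arise on a condom are not fixed by design. They depend on how quickly four records accumulate and on whether the couple then stops. If that differs by condom, the share of subjects with an event will differ too, even when the risk per day or per use is the same.

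The documents contain one concrete route. In the diary (SAP 9.1), an act without ejaculation is a listed reason for having no IELT record, and such an act does not count towards the four. The test condoms are meant to delay ejaculation. If they also produce more acts without a record, their periods need more uses and more days. Other routes could work in the opposite direction, for example a condom that couples prefer not to keep using.

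At stake is the between-condom reading of the safety tables. A reader given only percentages could not separate a difference in risk from a difference in exposure.

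**Working it through.** **1. The plan's own figure.** Protocol 4.1 gives a maximum participation of 19 weeks. 28 baseline days + 3 × (28 + 7) = 133 days = 19 weeks, so it reproduces. It also fixes the longest observation on one condom at 28 + 7 = 35 days. The documents give no adverse event rate and no expected period length by condom, so the risks and shifts below are assumptions shown as ranges.

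**2. Range of exposure in periods 1 and 2.** Shortest: four acts 24 hours apart span 3 × 24 = 72 hours. Adding the 3-day washout gives about a week, with 4 uses. Longest: 35 days with 8 uses.

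**3. Sensitivity of a per-subject proportion to exposure.** For events that accrue with time, let r be the risk per 28 days, λ = −ln(1 − r)/28 and P(d) = 1 − exp(−λd):

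| r per 28 days | 7 days | 14 days | 28 days |
|---|---|---|---|
| 5% | 1.3% | 2.5% | 5.0% |
| 10% | 2.6% | 5.1% | 10.0% |
| 20% | 5.4% | 10.6% | 20.0% |

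For events caused by use, with risk p per condom, P(k) = 1 − (1 − p)^k:

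| p per use | 4 uses | 8 uses |
|---|---|---|
| 0.5% | 2.0% | 3.9% |
| 1% | 3.9% | 7.7% |
| 2% | 7.8% | 14.9% |

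These tables show how far a proportion moves with exposure. They do not show a difference between condoms.

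**4. Difference between condoms at equal risk.** Simulation of 400,000 couples. Each couple has its own pace, shared across condoms, with a mean gap of 4 days between acts and at least 1 day. The period ends at 4 records, 28 days or 8 condoms, whichever comes first, and 3 days of washout are added. Every couple is assumed to stop as soon as it has four records. On one condom a share q of acts gives no record; on the other, none.

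| q | Mean window, days (comparator 17.6) | Mean uses (comparator 3.80) | Spurious difference, r = 5% | r = 10% | r = 20% |
|---|---|---|---|---|---|
| 0 | 17.6 | 3.80 | 0.0 points | 0.0 | 0.0 |
| 10% | 18.8 | 4.15 | 0.2 | 0.4 | 0.8 |
| 20% | 20.1 | 4.54 | 0.4 | 0.9 | 1.7 |
| 30% | 21.5 | 4.98 | 0.7 | 1.4 | 2.6 |

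The row q = 0 is the important control: pace varies widely between couples, and the expected difference is nil.

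For use-driven events, applying a 1% risk at the mean number of uses in the last row gives 1 − 0.99^4.98 = 4.88% against 1 − 0.99^3.80 = 3.75%, a difference of 1.13 points.

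**5. Days and uses need not move together.** If one condom instead makes the random part of each gap 25% longer, the mean window rises from 17.6 to 19.4 days while mean uses fall from 3.80 to 3.68. At r = 10% the time-driven difference is 0.6 points upward. Use-driven events would shift slightly downward. One denominator therefore cannot stand in for the other.

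**The case against.** A reader might infer that, because the window can vary five-fold (7 to 35 days), the condom with longer periods shows more events by construction. The documents do not support that. Each couple is meant to use all three condoms in one of six sequences, randomised in blocks of 6 (SAP 12.8), so its own pace cancels in expectation, as step 4 confirms. Bias needs a condom that changes its own exposure, and nothing in the documents shows that one does.

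Large figures can be produced by assumption. With a 10% risk per 28 days, suppose 60% of couples stop early on one condom and 20% on another, with windows of 7 and 31 days. The proportions are then 6.0% and 9.3%. But no such split is in the documents, and 7 days is the extreme: the entry criterion is four acts in four weeks. With a 17-day early window (two acts a week plus washout), the same split gives 8.1% and 10.0%.

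Three further points stand:
- The known common reactions are local (Protocol section on benefits and risks), so they plausibly follow use, and use ranges only about two-fold between 4 and 8 condoms.
- The adverse event output is descriptive, event counts are given beside proportions, and episodes per condom type are summarised (Protocol 9.5.3), so exposure is not invisible.
- The synopsis and Protocol 7.3 do call four weeks a maximum, so the fixed-length wording elsewhere may be shorthand.

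Against this, Protocol 9.5.2 does place the adverse event proportion among endpoints compared with control. No planned table relates events to condoms used or days at risk.

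**Conclusion.** The point holds in a conditional form. Exposure per condom is variable, and adverse events are reported by condom without reference to it. If a condom changes the pace or the number of acts needed for four records, the proportions can differ with no true difference in risk.

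Under the assumptions of step 4, the size is about 0.4 to 2.6 percentage points for a background risk of 10% to 20% per 28 days, and 0.2 to 0.7 points at 5%. For a 1% risk per use, the outer limits are 3.9% after four uses and 7.7% after eight. The direction cannot be foreseen.

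This is a reporting weakness in a descriptive safety analysis that is cheap to repair. It is not evidence that the safety comparison is biased, and it does not affect the sample size, the success criterion or the primary analysis.

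**What to change.** In Tables 14.2.2.26 and 14.3.1.1, by condom type and separately for males and females:
- Keep the proportions, with subjects exposed to that condom as the denominator. SAP 8 already analyses the safety population by treatment received, but the formula in SAP 10.5 divides by all subjects.
- Add treatment-emergent adverse events and device effects per 100 condoms used, the kind of denominator SAP 10.5 already uses for clinical failure, and per 100 couple-weeks at risk.
- Assign each event to the condom last used, including during washout. Count time at risk to match: from first use of that condom to first use of the next, or to the last visit.
- Show condoms used and days at risk by condom type next to the adverse event tables.

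State in the SAP that proportions and adjusted rates are read together. The adjusted rates should not replace the proportions: exposure is itself a post-randomisation outcome, and rates per couple-week assume a roughly constant hazard and include washout days without a test condom.

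The passages that describe a period of 4 weeks (Protocol 3.2 and 6.3) and those that allow an earlier visit (7.4 and 7.5) should be reconciled.

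Cost: SAP wording and a few table columns, from data already collected.
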